**Table 1: Schedule of Assessments**

Periods	Screening a	Treatment			Follow-up b		ET	
Visit/Timepoint or Duration	Prior to study drug initiation	Dosing		Taper	Study Drug Discontinuation without Taper	In-patient Follow-up	Weekly follow-up (Week 2, 3, & 4)	Early Termination
Day -1 to Day 1 Pre-dose through screening	Day 1 Study Drug Initiation 0 hours through 24 hours post study drug initiation	Day 2 24 hours through 36 hours post study drug initiation	Day 2 12-hours Starts at 36-hours post study drug initiation	Collected prior to or as close to study drug discontinuation as possible	Day 3 Or Starts as soon as study drug administration ends, lasts 24 hours	7 ±3, 14 ±3, and 21 ±3 days post last visit	Collected prior to or as close to study drug discontinuation as possible	

m. Neurosteroid levels (venous or arterial) blood samples will be collected pre-dose (screening) and at 24-hours (+/- 1 hour) of study drug initiation. If study drug is discontinued during this 24 hours, the second sample should be collected prior to study drug discontinuation, if feasible. NS samples cannot be collected from the study drug infusion line. The location of study drug access and location of NS sample collection should be documented in the subject's source.

n. Blood gas including FiO2, PaO2, and Arterial pH, if collected per the investigator's discretion for subject's care, from the time of SE diagnosis through the in-patient follow-up day. If no samples are collected, a sample is not required. In addition, a blood gas sample should be collected when the decision is made to intubate the subject occurring after start of study drug infusion through the in-patient follow-up day. The sample should be collected immediately prior to or as close as possible to the time of intubation.

o. If a subject has a lumbar puncture for the collection of cerebral spinal fluid (CSF) per investigator's discretion as part of their care and there is adequate volume, a sample will be aliquoted for future analysis of ganaxolone. If multiple lumbar punctures are performed, a sample from each puncture is requested. If not collected or not enough CSF is collected to provide a sample for the study, a sample is not required.

p. CGI-S is collected pre-dose (screening) and 36-hours (+/- 1-hour) after study drug initiation. Collect at time of study drug discontinuation, either at the end of the study drug taper or if the study drug administration is stopped without a taper and 24-hours (+/- 1-hour) after study drug discontinuation. Collect at the week 2, 3, and 4 follow-up visits/contacts. If possible, for subjects who early terminate from the study, collect at the time early termination is being considered and as close as possible to the end of the study drug administration. Collect any time, if medically indicated, per investigator's judgment.

q. CGI-I is collected within 2 hours of study drug initiation and 36-hours (+/- 1-hour) after study drug initiation. Collect at time of study drug discontinuation, either at the end of the study drug taper or if the study drug administration is stopped without a taper and 24-hours (+/- 1-hour) after study drug discontinuation. Collect at the week 2, 3, and 4 follow-up visits/contacts. If possible, for subjects who early terminate from the study, collect at the time early termination is being considered and as close as possible to the end of the study drug administration. Collect any time, if medically indicated, per investigator's judgment.

r. Status Epilepticus and Seizure Questions should be collected at 15-minutes (+/- 5-min), 30-, 60-minutes (+/- 15-min), 2-, 4-, 6-, 8-, 10- 12- 18- (+/- 30-minutes) and 24- and 36- hours (+/- 1-hour) after study drug initiation. Collect at the time of study drug discontinuation, either at the end of the study drug taper or if the study drug is stopped without a taper and 24-hours (+/- 1-hour) after study drug discontinuation. Collect at the week 2, 3 and 4 follow-up visits/contacts. If possible, for subjects who early terminate from the study, collect at the time early termination is being considered and as close as possible to the end of the study drug administration.

s. Intubation Question should be collected at 18- (+/- 30-min), 24- and 36-hours (+/- 1 hours) after study drug initiation. Collect at time of study drug discontinuation, either at the end of the study drug taper or if the study drug administration is stopped without a taper and 24-hours (+/- 1-hour) after study drug discontinuation.

t. MRS is collected at the time of study drug discontinuation, either at the end of the study drug taper or if the study drug administration is stopped without a taper and 24-hours (+/- 1-hour) after study drug discontinuation. Collect at the week 2, 3, and 4 follow-up visits/contacts. If possible, for subjects who early terminate from the study, collect at the

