- a. Pre-dose (screening) and 36-hours (+/- 1-hour) after study drug initiation,
- b. Time of study drug discontinuation, either at the end of the study drug taper or if the study drug administration is stopped without a taper and
- c. 24-hours (+/- 1-hour) after study drug discontinuation.
- d. Week 2, 3, and 4 follow-up visits (in-person or via telephone call).
- e. If possible, for subjects who early terminate from the study, collect at the time early termination is being considered and as close as possible to the end of the study drug administration.
- f. Any time, if medically indicated, per investigator's judgment.

CGI-I is collected at:

- a. Within the first 2 hours of study drug initiation and 36-hours (+/- 1-hour) after study drug initiation,
- b. Time of study drug discontinuation, either at the end of the study drug taper or if the study drug administration is stopped without a taper and
- c. 24-hours (+/- 1-hour) after study drug discontinuation.
- d. Week 2, 3, and 4 follow-up visits (in-person or via telephone call).
- e. If possible, for subjects who early terminate from the study, collect at the time early termination is being considered and as close as possible to the end of the study drug administration.
- f. Any time, if medically indicated, per investigator's judgment.

14. Modified Rankin Scale (MRS) should be collected at:

- a. Time of study drug discontinuation, either at the end of the study drug taper or if the study drug administration is stopped without a taper and
- b. 24-hours (+/- 1-hour) after study drug discontinuation.
- c. Week 2, 3 and 4 follow-up visits (in-person or via telephone call).
- d. If possible, for subject's who early terminate from the study, collect at the time early termination is being considered and as close as possible to the end of the study drug administration.
- e. Any time, if medically indicated, per investigator's judgment.

15. Status Epilepticus and Seizure Questions should be collected at:

- a. 15-minutes (+/- 5-min), 30-, 60-minutes (+/- 15-min), 2-, 4-, 6-, 8-, 10-, 12-, 18- (+/- 30-min), and 24- and 36-hours (+/- 1 hour) after study drug initiation,
- b. Time of study drug discontinuation, either at the end of the study drug taper or if the study drug administration is stopped without a taper and
- c. 24-hours (+/- 1-hour) after study drug discontinuation.
- d. Week 2, 3, and 4 follow-up visits (in-person or via telephone call).

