#### **Secondary Endpoints:**

- For subjects on concomitant second-line therapy: time to cessation of SE or next treatment decision (defined as the need for an IV anesthetic drug (a 3rd line treatment) when on ganaxolone)
- Level of responsiveness as assessed by the GCS, Four Score Scale, and RASS at 24 hours post study drug initiation
- The number of subjects who did not require additional 2nd line IV AED therapy for SE treatment in the 24-hours after study drug taper
- Safety and tolerability of IV ganaxolone as adjunctive SE therapy as assessed by neurologic, EEG, physical examinations, clinical laboratory tests, ECGs, vital signs, and AEs
- Number of subjects who maintained SE resolution 24 hours after study drug taper and at Week 4
- Number of subjects with seizure(s) following the cessation of SE through the in-patient follow-up day
- Seizure burden assessed as duration of electrographic seizure activity per hour of EEG recording collected
- Clinical outcome as assessed by MRS at the in-patient follow-up day and Week 4
- Characterization of the pharmacokinetic profile of ganaxolone IV solution in SE subjects
- Length of stay in intensive care unit and hospital, mortality, morbidity, need for and duration of intubation and mechanical ventilation, and seizure freedom

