**Table 1: Schedule of Assessments**

Periods	Screening a	Treatment			Follow-up b		ET	
Visit/Timepoint or Duration	Prior to study drug initiation	Dosing		Taper	Study Drug Discontinuation without Taper	In-patient Follow-up	Weekly follow-up (Week 2, 3, & 4)	Early Termination
	Day -1 to Day 1 Pre-dose through screening	Day 1 Study Drug Initiation 0 hours through 24 hours post study drug initiation	Day 2 24 hours through 36 hours post study drug initiation	Day 2 12-hours Starts at 36-hours post study drug initiation	Collected prior to or as close to study drug discontinuation as possible	Day 3 Or Starts as soon as study drug administration ends, lasts 24 hours	7 ±3, 14 ±3, and 21 ±3 days post last visit	Collected prior to or as close to study drug discontinuation as possible
Study Drug infusion k		✓	✓	✓				
Pharmacokinetic blood sampling l		✓	✓	✓	✓	✓		
Neurosteroid levels m	✓	✓						
Blood Gas n	✓							
Cerebral Spinal Fluid o	✓							
Clinical Global Impression of Severity (CGI-S) p	✓		✓	✓	✓	✓	✓	✓
Clinical Global Impression of Improvement (CGI-I) q		✓	✓	✓	✓	✓	✓	✓
SE & Seizure Questions r		✓	✓	✓	✓	✓	✓	✓
Intubation Question s		✓	✓	✓	✓	✓		
Modified Rankin Scale (MRS) t				✓	✓	✓	✓	✓

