## 1. BACKGROUND INFORMATION

### 1.1 Indication and Current Treatment Options

Status epilepticus (SE) is a highly serious occurrence within the spectrum of epileptic disorders that is characterized by the manifestation of continuous or intermittent seizures lasting more than 5 minutes in duration without full recovery of consciousness or 10 minutes of continuous seizure activity on EEG, or intermittent paroxysmal activity for more than 50% of an hour.

If SE is not treated immediately, prolonged seizure activity can result in permanent neuronal damage and contribute to the high morbidity and mortality associated with SE. Paroxysmal hypersynchronous electrical discharges occur when there is too much excitation or too little inhibition in the area of the brain where the abnormal discharge starts. Gamma-aminobutyric acid (GABA) is recognized as the principal inhibitory neurotransmitter in the cerebral cortex, and a disturbance in GABA-mediated functions results in the occurrence of epileptic seizures. SE is often caused by pre-existing epilepsy, but it can also be caused by cerebral damage. In subjects with chronic epilepsy, low blood concentrations of antiepileptic drugs (AEDs) can lead to SE. Other recognized causes of SE include, but are not limited to, cerebrovascular accidents, anoxia or hypoxia, metabolic causes, and alcohol and drug withdrawal.

A growing body of evidence from research and clinical observation supports the concept that SE becomes more difficult to control as its duration increases, and prolonged SE and refractoriness to treatment are associated with poor prognosis. Resistance to treatment has been partially attributed to the internalization of postsynaptic GABAA receptors and externalization of glutamate receptors. It has also been postulated that resistance may occur because of a mechanistic shift from inadequate GABAergic inhibitory receptor-mediated transmission to excessive N-methyl-D-aspartic acid excitatory receptor-mediated transmission. Because prolonged epileptiform bursting results in a reduction of GABAA-mediated synaptic inhibition, antiepileptic treatments that rely on enhancing intrasynaptic GABAA neurotransmission become less effective the longer SE continues.

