SE can be classified into three subtypes: generalized convulsive SE (GCSE), non-convulsive SE (NCSE), and refractory SE (RSE). GCSE is characterized by convulsions that are associated with tonic-clonic movements of the extremities and mental status impairment, and may result in focal neurologic deficits lasting hours to days following an episode. NCSE is defined as seizure activity seen on electroencephalography (EEG) without clinical symptoms; however, acutely ill subjects may present with impaired mental status following an NCSE episode. RSE occurs in subjects who do not respond to the standard SE treatment regimen of a benzodiazepine and a secondary AED.

SE is a neurologic emergency that requires aggressive treatment to stop the seizures and prevent permanent neuronal damage. Mortality due to SE can range from 3% to 40% depending on etiology, age, status type, and status duration. Previous studies have shown that seizures cause neuronal death via excitotoxic mechanisms as a result of excessive neuronal firing. Furthermore, GCSE is associated with many complications, including cardiac arrhythmias, rhabdomyolysis, pulmonary edema, electrolyte and glucose imbalance, and temperature disturbances.

The prognosis worsens and the mortality increases for subjects whose SE develops into RSE or super-refractory SE (SRSE). Approximately one-third of subjects with RSE and SRSE will die of their condition; one-third recover but with chronic neurologic or other deficits, and one-third have been generally described as returning to baseline. The longer subjects are kept in a long-term medically-induced coma to stop the seizures, the worse the prognosis.

As SE is a medical emergency, the primary goal of treatment is to rapidly stop the seizures and avoid complications. Treatment typically occurs in stages: emergent initial therapy (first-line), urgent control therapy (second-line), and refractory therapy (third-line). Therefore, continuous video-EEG monitoring is critical for monitoring sedation as well as SE outcome.

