#### **7.2.3.7      Modified Rankin Scale (MRS)**

The MRS is a commonly used 6-point scale for measuring the degree of disability or dependence in the daily activities of people who have suffered a stroke or other causes of neurology disability. The MRS should be assessed at the timepoints noted in Table 1.

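### No pre-SE MRS is scheduled, so the secondary clinical-outcome endpoint cannot separate new disability from return to the pre-SE state

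*Protocol*

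**What the plan says.** The synopsis and Section 9.7.2 list the secondary endpoint "Clinical outcome as assessed by MRS at the in-patient follow-up day and Week 4". It is stated as a level, not as a change.

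The MRS schedule appears in three places, and all three begin at the end of dosing. Footnote t of Table 1 reads "MRS is collected at the time of study drug discontinuation, either at the end of the study drug taper" and continues with 24 hours later and Weeks 2, 3 and 4. Item 14 of the synopsis assessments ("Modified Rankin Scale (MRS) should be collected at") gives the same list. The MRS row of Table 1 has no tick for screening, Day 1 or Day 2 dosing. Section 7.2.3.7 adds no rating of its own: "The MRS should be assessed at the timepoints noted in Table 1".

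On the population, Section 1.1 says "SE is often caused by pre-existing epilepsy, but it can also be caused by cerebral damage". On outcome after refractory and super-refractory SE, the same section says about one-third die, and of the others "one-third recover but with chronic neurologic or other deficits, and one-third have been generally described as returning to baseline".

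**The concern.** MRS grades disability in daily life, which a subject may have had before the episode. Section 1.1 names epilepsy and cerebral damage as causes of SE, and no eligibility criterion names prior disability. Section 4.2 excludes anoxic injury, and traumatic brain injury less than 24 hours old, as the primary cause of SE. Older injury or stroke is not listed.

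The protocol itself describes survivors as either left with deficits or back at baseline. A Week 4 MRS level cannot make that distinction. A subject with old disability who recovers fully to the earlier state gets the same score as one newly disabled to the same degree. The pre-SE state may be hard to reconstruct later if nobody records it during the stay.

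**Working it through.** **1. Is a pre-SE MRS collected under any heading?** No. Synopsis item 14, the Table 1 row and footnote t all start at study drug discontinuation, and Section 7.2.3.7 points back to Table 1. The allowance for extra ratings when medically indicated does not supply a pre-SE value.

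**2. Does another item grade prior function?**
- STESS (Section 7.2.2.2) uses age, seizure history, seizure type and consciousness.
- Medical history (Section 7.2.3.1) covers illnesses, surgeries, medications, family history, substance use and seizure or SE history. It has no functional grade.
- GCS, RASS, FOUR and CGI-S do have pre-dose values; for example, "CGI-S is collected pre-dose (screening) and 36-hours (+/- 1-hour) after study drug initiation". These are taken during SE, so they describe the acute state.
- The SAP's general baseline (Section 4.4) is the last assessment before dosing. No scheduled MRS meets it, and one rated during SE would not be a pre-SE value anyway.

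**3. How would MRS be analysed?** Protocol Section 9.8 plans a summary by treatment group and visit. The covariates in Section 9.7.1 (age, GCS, history of epilepsy) belong to the primary endpoint and do not include prior function.

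**4. Plan figures.** There is none to reproduce. N=242 and the power table in Section 9.5 concern the primary endpoint.

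**5. Illustration for an uncontrolled group.** Assumptions, not in the documents: a share q is already in a poor MRS band before SE and stays there, and the rest have a risk r = 30% of entering it. Observed poor = q + (1 − q)r. Share that predates SE = q / observed. For q = 20%: 0.20 + 0.80 × 0.30 = 0.44, and 0.20 / 0.44 = 45%.

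| q | Observed poor | Share predating SE |
|---|---|---|
| 10% | 37% | 27% |
| 20% | 44% | 45% |
| 30% | 51% | 59% |
| 40% | 58% | 69% |

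The risk of new poor outcome among those not already in the band is 30% in every row. Only the mix of subjects changes.

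**6. Illustration for a 1:1 comparison.** Assumptions: 121 per arm, fixed design, one-sided 0.025, and new poor outcome of 60% versus 40% in subjects not already in the band. The 20-point size is borrowed from Section 9.5; the protocol states no MRS effect. The arm rates are q + (1 − q) × 0.60 and q + (1 − q) × 0.40, so the difference is (1 − q) × 0.20. Power = Φ[(Δ − 1.96 × √(2p̄(1 − p̄)/n)) / √((p₁(1 − p₁) + p₂(1 − p₂))/n)].

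For q = 20%: rates 0.68 and 0.52, p̄ = 0.60. The null term is 1.96 × √(0.48/121) = 0.123 and the denominator is √(0.4672/121) = 0.062, giving Φ(0.59) = 72%.

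| q | Arm rates | Difference | Power |
|---|---|---|---|
| 0% | 60% v 40% | 20 points | 88% |
| 10% | 64% v 46% | 18 points | 81% |
| 20% | 68% v 52% | 16 points | 72% |
| 30% | 72% v 58% | 14 points | 63% |
| 40% | 76% v 64% | 12 points | 53% |

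The difference shrinks but keeps its sign. That is dilution.

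**The case against.** The strongest reply is that little depends on this. MRS serves one descriptive secondary endpoint. The SAP is written on Amendment 3, whereas the protocol's summary of changes shows MRS arriving with Amendment 4. The SAP's clinical-outcome endpoint names no scale, its schedule has no MRS row, and its Section 4.8 has no MRS analysis. All of this stands. It places the defect in the protocol's data collection, not in an analysis now planned.

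Three stronger readings are tempting, and the documents do not support them.

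- A reader might infer that MRS alone was left without a reference value. MMSE has no pre-dose value either; Table 1, footnote f, starts it when the subject's own consent or assent is sought. The pre-dose GCS, FOUR, RASS and CGI-S values are not pre-SE values.
- A reader might infer that differences in prior disability between the three dose cohorts would pass for dose effects. The cohorts exist only in the SAP, with targets of 713, 650 and 500 mg/day. Day 1 under Amendment 4 for subjects of at least 40 kg totals 30 + 80 × 2 + 40 × 10 + 20 × 12 = 830 mg, which matches none of them. No document plans MRS by cohort.
- A reader might infer bias between arms. Under 1:1 randomisation prior disability is balanced in expectation, so the loss is in effect size and precision.

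**Conclusion.** The gap is confirmed and of modest weight. The scale named for clinical outcome has no scheduled pre-SE rating, and nothing else collected fills the gap. An MRS level therefore cannot separate new disability from return to the pre-SE state. For an uncontrolled open-label group, the Week 4 level cannot be attributed to the episode. For the planned randomised comparison, the cost is dilution and lost precision.

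The primary endpoint and the sample size of 242 are untouched. The size of the effect on MRS is unknown: the documents give neither a prevalence of prior disability nor an MRS cut. The shares and power values above show only how the problem scales with q. A reader might turn them into a number of affected open-label subjects, but the documents support no such count. The ceiling of about 30 also includes subjects enrolled before Amendment 4 added MRS.

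**What to change.** Add one retrospective pre-SE MRS, meaning status before the current episode, to the screening column of Table 1 and to footnote t. Take it from the chart, the LAR or the subject, within the time footnote c already allows for medical history (up to the end of the taper). State that it is the reference value for MRS. A rating entered after dosing would otherwise fail the SAP's general baseline rule, and a rating of the subject's state during SE would not serve.

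Report the raw MRS distribution at each visit together with the number of subjects back to the pre-SE score or better. Count deaths as not returned; the protocol does not say how they enter the MRS summary. In any between-group comparison, adjust for the pre-SE score.

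The cost is one eCRF field per subject, often from an informant already giving consent and history, plus a short addition to the analysis text. The downside is some recall error in the pre-SE score.

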**Table 1: Schedule of Assessments**

Periods	Screening a	Treatment			Follow-up b		ET	
Visit/Timepoint or Duration	Prior to study drug initiation	Dosing		Taper	Study Drug Discontinuation without Taper	In-patient Follow-up	Weekly follow-up (Week 2, 3, & 4)	Early Termination
	Day -1 to Day 1 Pre-dose through screening	Day 1 Study Drug Initiation 0 hours through 24 hours post study drug initiation	Day 2 24 hours through 36 hours post study drug initiation	Day 2 12-hours Starts at 36-hours post study drug initiation	Collected prior to or as close to study drug discontinuation as possible	Day 3 Or Starts as soon as study drug administration ends, lasts 24 hours	7 ±3, 14 ±3, and 21 ±3 days post last visit	Collected prior to or as close to study drug discontinuation as possible

time early termination is being considered and as close as possible to the end of the study drug administration. Collect any time if medically indicated, per investigator's judgment.

u. AEs and concomitant medications will be collected throughout the study; non-direct questioning will occur. The collection requirements will differ depending on the subject's treatment progression as follows: 1. All adverse events and associated concomitant medications will be collected through the in-patient follow-up day. 2. IV anesthetic agents (midazolam, propofol, thiopental, pentobarbital, or ketamine) administered during the study drug treatment period and the in-patient follow-up day should be followed through the week 4 visit/contact. 3. During the weekly follow-up visits, only ongoing AEs and new AEs assessed by the investigator to be related to study drug will be recorded and the concomitant medications associated with these AEs. 4. In addition, during the weekly follow-up visits, AEs of urinary tract infection (UTI), hospital-acquired/ventilator-associated pneumonia, myocardial infarction (MI), sepsis from any source, critical illness myopathy/neuropathy, significant hypotension requiring support of vasopressors will be recorded regardless of relatedness. Associated concomitant medications for these AEs will not be recorded. 5. All SAEs regardless of relationship to study drug and their associated concomitant medications will be recorded from the time of 1st dose through the last follow-up visit/contact. 6. For subjects who early terminate from the study, prior to discontinuation as much information as is available should be recorded for ongoing AEs/SAEs, new AEs/SAEs and their associated concomitant medications, especially those that may have led to the early termination.

